10.4. Method of Blinding

Open label to participants and the investigators, with the exception of the ultrasonographers who are undertaking the scoring for the primary trial outcome. Scoring will be undertaken remotely from the participant being examined, via a video link of the structured ultrasound examination, without audio, and the technicians who are undertaking the egg counts for the secondary outcome.

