26.2.1. Required Documentation	
26.2.1. Procedure for initiating/opening a new site	40
26.2.3. Principal Investigator Responsibilities	40
26.3. APPENDIX 3 - PROTOCOL AND AMENDMENT HISTO	ORY41
26.4. Safety Reporting Flow Chart	48

3. Abbreviations

AE/AR	Adverse event/Adverse Reaction
CA	Competent Authority
ССТИ	Cambridge Clinical Trials Unit
CRF	Case Report Form
CTIMP	Clinical Trial of Investigational Medicinal Product
UCam	University of Cambridge
DSUR	Development Safety Update Report
GCP	Good Clinical Practice
ICF	Informed Consent Form
IMP	Investigational Medicinal Product
MDA	Mass Drug Administration
NHS	National Health Service
NTD	Neglected Tropical Disease
PIS	Participant Information Sheet
PZQ	Praziquantel
R&D	Research and Development
RA	Regulatory Agency
REC	Research Ethics Committee
SAE/SAR	Serious Adverse Event/Serious Adverse Reaction
SCORE	Schistosomiasis Consortium for Operational Research and Evaluation
SUSAR	Suspected Unexpected Serious Adverse Reaction
TMG	Trial Management Group
TSC	Trial Steering Committee
VCD	Vector Control Division

[figure not shown]
4. Trial Synopsis

Title of clinical trial	Impact of increased praziquantel frequency on childhood fibrosis in persistent schistosomiasis morbidity hotspots. A phase IV CTIMP trial.
Sponsor name	Cambridge University Hospitals NHS Foundation Trust and University of Cambridge
ISRCTN Number	16994599
Medical condition or disease under investigation	Periportal fibrosis of the liver caused by schistosomiasis mansoni
Purpose of clinical trial	To ascertain the most effective treat- ment frequency for morbidity control
Primary objective	To compare the effect of 2x and 4x treatments annually with praziquantel to the standard 1x annual treatment on the prevalence of Schistosoma mansoni associated periportal fibrosis of the liver.
Secondary objective (s)	To compare the effect of 2x and 4x treatments annually with praziquantel to the standard 1x annual treatment on the mean infection intensity of Schistosoma mansoni.
Trial Design	Phase IV, single centre, randomised, trial, single blinded to the primary outcome assessors, but open label to all other investigators and participants.
Trial Outcome Measures	Ultrasound periportal fibrosis pattern scores.
Sample Size	600

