8.1. Statement of Design

This is a phase IV, randomised superiority trial that is blinded to the primary outcome assessors, but open label to all other investigators and participants.

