8.6. Trial Outcome Measures

8.6.1. Primary outcome measure

The primary outcome is prevalence of periportal fibrosis, defined as Niamey Protocol pattern scores of C, D, E or F, measured at 2-years post 1st treatment follow-up.

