8.6.2. Secondary outcome measure

The secondary outcome is *Schistosoma mansoni* infection intensities as measured by Kato-Katz faecal egg counts (28), measured at 2-years post 1st treatment follow-up.

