10.3. Treatment Assignment and Randomisation Number

Prior to enrolment trial participant identification numbers will be generated and these numbers assigned an intervention arm via simple computer generated random number randomisation. This paper-based list will be provided to the trial site team and upon enrolment children will be assigned to the ordered participant identification numbers, class-by- class and school-by-school or household or household if schools are not open and school-by-school. Randomisation will be stratified by school.

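### Section 10.4 masks the remote ultrasound scorer but does not require masking of the on-site operator who acquires the images for the primary outcome

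*Protocol*

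**What the plan says.** Four places in the protocol bear on masking.

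- **Section 8.1** describes the trial as "blinded to the primary outcome assessors, but open label to all other investigators and participants". The synopsis (section 4) says nearly the same: "single blinded to the primary outcome assessors, but open label to all other investigators and participants".
- **Section 10.4**, the operative section, sets the default and one exception: "Open label to participants and the investigators, with the exception of the ultrasonographers who are undertaking the scoring for the primary trial outcome". It then says how the scorer is kept apart from the child: "Scoring will be undertaken remotely from the participant being examined, via a video link of the structured ultrasound examination, without audio". The same sentence goes on, without parsing, "and the technicians who are undertaking the egg counts for the secondary outcome". The natural reading is that these technicians belong with the masked staff.
- **Section 10.3** has identification numbers assigned to arms before enrolment, and says of the result: "This paper-based list will be provided to the trial site team".
- **Sections 8.6.1 and 8.6.2** define the outcomes. For the first, "The primary outcome is prevalence of periportal fibrosis, defined as Niamey Protocol pattern scores of C, D, E or F". The secondary outcome is "infection intensities as measured by Kato-Katz faecal egg counts (28), measured at 2-years post 1st treatment follow-up".

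Section 12.3.1 requires the ultrasound examinations to follow the WHO Niamey Protocol. Section 12 has annual doses given after the scan, and has the trial team dispense the doses in between.

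**The concern.** A remote scorer on a silent link is well shielded from hearing or seeing which arm a child is in. The score, however, is read from images that another person obtains. The exception in 10.4 covers those who do the scoring. The operator beside the child does not score, so falls under the open-label default, or at the least is not required to be masked.

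By the 2-year scan the arms differ by 2, 4 or 8 earlier doses (section 11.1 gives totals of 3, 5 and 9, each including one final dose after the scan). An operator who knows this could, without intending to, look for mild fibrosis with more or less persistence. The cut that defines the primary outcome lies at that mild end. In the screening data in section 6.1, 82% of children had fibrosis and 31% had central fibrosis, so 82 - 31 = 51 points, or 51/82 = 62% of positives, had no central fibrosis. Any such influence would be differential misclassification of the primary endpoint, and a masked reader does not correct for what was not shown.

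**Working it through.** **Who is masked, section by section**

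| Person | 8.1 and synopsis | 10.4 |
|---|---|---|
| Remote scorer | masked | masked |
| On-site operator acquiring images | not in the masked group | not in the exception |
| Egg-count technicians | not named; the outcome they read is secondary | apparently masked (broken sentence) |

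The second row is the substantive point. It follows from the default and the narrow exception; no section states the operator's status outright.

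**The plan's own figure first.** Inputs from 17.1 and 17.2: 80% C-F in the control arm, an absolute reduction of 20 points, 150 per arm, two-sided 1.66%, so z = 2.395.

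- Standard error under the null, with pooled rate 0.70: sqrt(2 × 0.21/150) = 0.0529.
- Standard error under the alternative: sqrt((0.16 + 0.24)/150) = 0.0516.
- Power: P(Z < (0.20 - 2.395 × 0.0529)/0.0516) = P(Z < 1.42) = 92%, as stated.
- Enrolment: 450/(1 - 0.25) = 600, as stated.

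The point made here changes neither figure.

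**Illustration of what an acquisition effect would do.** Assumptions not in the documents: no true effect, and a share m of the true C-F children in the four-times-yearly arm shown as A/B because of how the images were obtained, with no such loss in the control arm. The spurious difference is d = m × 80 points. The chance that this one comparison falsely favours the four-times-yearly arm is P(Z > 2.395 - d/SE).

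- m = 0: 1.66%/2 = 0.8%.
- m = 5%, d = 4 points (80% v 76%): SE = sqrt((0.16 + 0.1824)/150) = 0.0478; P(Z > 2.395 - 0.837) = P(Z > 1.56) = about 6%.
- m = 10%, d = 8 points (80% v 72%): SE = sqrt((0.16 + 0.2016)/150) = 0.0491; P(Z > 2.395 - 1.629) = P(Z > 0.77) = about 22%.

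Counting rejections in either direction, assumed shifts of 2, 5 and 10 points give about 2.7%, 8.8% and 35%, against a nominal 1.66%.

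**The case against.** The strongest reply has four parts.

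1. **The operator's knowledge is inferred.** The protocol does not say who holds the probe, or that this person knows the arm or sees the list. Section 10.3 provides the list for assigning numbers at enrolment; it does not put it at the scanning station. This stands. The finding is that masking of the operator is not required, not that the operator is known to be aware of the arm.

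2. **The examination is structured.** It follows the Niamey Protocol, and a masked scorer may well notice a required view that is missing or cut short. This also stands in part. A reader might infer that the scorer could never detect biased acquisition, and the documents do not support that. What remains is subtler variation in how the required views are obtained.

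3. **The shifts are arbitrary and small beside the 20-point success criterion in 15.1.1.** The 5% and 10% rates have no source in the documents, and placing every lost case in one arm is the unfavourable assumption. A spurious 4 or 8 points alone would not reach 20. The formal test in 17.1, however, has no 20-point margin: at 80% v 68% the standard error is sqrt((0.16 + 0.2176)/150) = 0.0502, so an observed difference of about 2.395 × 0.0502 = 12 points is enough. A spurious shift would also add to any true effect in the estimate.

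4. **The egg counters are masked.** A reader might infer from 8.1 and the synopsis that the secondary outcome is read unmasked. The documents do not support that: 10.4 is the only section to address these technicians and it appears to mask them. The two summary lines speak of investigators, which need not include laboratory technicians. This part is a matter of wording.

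**Conclusion.** The concern holds in a limited form. Section 10.4 protects the reading of the images and, apparently, the egg counts. It leaves the acquisition of the images outside the required masking, in a trial where the site team holds the arm list. Knowledge of the arm can therefore reach the C-F versus A/B classification through the operator, with the structured examination as a partial safeguard.

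The size cannot be derived from the documents. Under the stated assumptions, a spurious 4 or 8 points would raise the chance of falsely favouring four treatments a year from 0.8% to about 6% or 22%. These figures show how sensitive the test is; they do not predict the bias. Sample size, power and significance level are unaffected. The operator point merits a change because the remedy is cheap and bears on the primary endpoint. The mismatch over the egg-count technicians is editorial.

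**What to change.** In section 10.4:

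- Extend the masking to the operator who acquires the images at the 2-year scan.
- Keep the list linking numbers to arms, and the treatment log, away from the scanning station.
- Present each child by identification number only, with no discussion of treatment during the scan.
- Where rostering allows, use existing staff who do not dispense the intervening treatments as operators.
- Rewrite the broken sentence so that the masking of the egg-count technicians is explicit.

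In 8.1 and the synopsis, name the same masked groups as 10.4.

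The cost is protocol wording and some separation of existing roles. No extra reader, visit or procedure is needed, since the annual doses already follow the scan. The downsides are a slight rostering constraint and the fact that children, who know their own schedule, may still reveal it. Masking of the operator would therefore be good but not complete.

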10.5. Participant Withdrawal Criteria

- Severe Adverse Reaction to praziguantel
- Withdrawal of consent/assent

11. Trial Treatments

11.1 Treatment Summary

Praziquantel, ~40mg/kg, dependent on standardised and verified dose pole, which was developed by WHO in 2001 for the administration of praziquantel without the use of weighing scales (29,30). Maximum dose 4x600mg tablets. Total treatments detailed below include an end of trial final treatment.

Control arm: 3 treatments (1x per annum for 2-years + final treatment)
Intervention arm 1: 5 treatments (2x per annum for 2-years + final treatment)
Intervention arm 2: 9 treatments (4x per annum for 2-years + final treatment)

11.1.1 Name and description of IMP X

Praziquantel. Anti-helmintic drug specific for trematode infections. It is distributed through MDA programmes in endemic countries through trained non-clinical community drug distributors. WHO estimates that 151M doses were dispensed through MDA programmes in 2017.

11.1.1.1 Legal status

Licensed for use in those over the age of 4-years. Licensed in Uganda. On the WHO Model List of Essential Medicines.

11.1.1.2. Supply

Praziquantel, the IMP, in the trial will be standard commercial stock as used by MDA programme, allocated by Vector-Control Division, Ministry of Health, from the praziquantel donated by Merck Healthcare KGaA for preventative chemotherapeutic treatment of school-aged children. Where possible this will be from a single manufacturing batch. The batch number and Certificate of Analysis, of all praziquantel donated by Merck Healthcare KGaA for use in this trial, along with manufacturing and expiry dates will be submitted for Clinical Trial Authorisation (CTA) to the National Drugs Authority (NDA) – Uganda, prior to its administration to trial participants.

In the event of supply interruption of the praziquantel, dontated by Merck Healthcare KGaA to the MDA, biosimilar praziquantel preparations, used by the MDA programme in Uganda are permitted for use in this trial.

11.1.1.3.Packing and Labelling

Provided in clearly labelled packages of tablets, as provided by the manufacturer, ready for dispensing according to a standardised dose pole. Administration will be observed.

11.1.1.4. Storage conditions

Praziquantel tablets are stable when stored at room temperature.

11.1.1.6.Maximum duration of treatment of a participant

At each treatment time-point participants will receive a single dose of praziquantel.

11.1.1.6.Dose

Praziquantel treatment will be assigned according to the WHO dose pole for praziquantel, a standardised and validated pole that assigns treatment according to height to facilitate mass-drug administration. The pole is designed to assign treatment doses of approximately 40mg/kg. The tablet is scored for easy breakage as doses include treatment with half tablets. The maximum dose dispensed for treatment of schistosomiasis is four 600mg PZQ tablets.

11.1.1.7.Administration

Oral, after provision of food.

11.1.1.8 Known drug reactions

Neurological

Headaches – very common (>10%)

Dizziness - very common (>10%)

Vertigo, drowsiness – common (1-10%)

Seizures – very rare (<0.01%)

Gastro-intestinal

Gastrointestinal and abdominal pains- very common (>10%)

Nausea – very common (>10%)

Vomiting – very common (>10%)

Anorexia – common (1 – 10%)

Diarrhoea – common (1 – 10%)

Bloody diarrhea - - very rare (<0.01%)

Dermatological

Urticaria – very common (>10%)

Cardiovascular

Unspecified arrhythmias – very rare (<0.01%)

Immune system disorders

Allergic reaction – very rare (<0.01%)

Polyserositis – very rare (<0.01%)

Eosinophilia – very rare (<0.01%)

Jarisch-Herxheimer reaction – very rare (<0.01%)

Hepatobiliary disorders

Liver function tests increased - rare (0.01 - 0.1%)

Musculoskeletal and connective tissue disorders

Myalgia – common (1 – 10%)

General disorders

Fatigue-very common (>10%)

Feeling unwell (asthenia, malaise) – common (1 – 10%)

Fever-common (1 - 10%)

Adverse reactions with food, over the counter drugs or commonly prescribed drugs are not reported.

11.1.1.9. Dose modifications

N/A

11.1.1.10. Procedures for monitoring treatment compliance

Treatment will be observed by a member of the study team trained in dispensing praziquantel. If the individual refuses treatment this will be entered into the treatment log.

11.2. Accountability and dispensing

11.2.1.Pharmacy responsibilities

The Vector Control Division – Ministry of Health, Uganda are responsible for ensuring adequate stocks of praziquantel. Praziquantel will be stored out of direct sunlight, with restricted access, prior to transport to the trial site. A trial team member will observe provision of treatment, which will be conducted in each participating school, local community trial site location or house-hold to house-hold by either the

teacher in each participating school who is the National Control Programme trained drug dispenser, an appropriately trained VHT or trial team member

11.2.2 Drug accountability

A log of drug treatments will be kept, including batch number, dose received, and date of treatment.

11.2.3 Returns and destruction

All praziquantel not used within the trial will be returned to Trial site co-ordinator, [name], Vector Control Division – Ministry of Health, Uganda.

12 Procedures and assessments

All procedures will be undertaken within the communities. Ultrasonography examinations and phlebotomy will be conducted within the schools or local community trial site location, when the schools are not available due to COVID-19 restrictions or any other government restrictions, including other infectious diseases. Stool and urine samples will be collected in a sensitive manner from participants in the school setting or house-hold to house-hold dependent upon COVID-19 or other government restrictions. Annual treatments will be dispensed after scheduled sample collection and ultrasonography examinations in the school setting, local community trial site location or house-hold to house-hold dependent upon COVID-19 or other government restrictions. Intervening treatments will be dispensed by the trial team during visits to the participating primary schools, community trial site location or house-hold to house-hold dependent upon COVID-19 or other government restrictions. Treatment will be observed by trained members of the trial team, and a 24-hour post-treatment follow-up will be conducted by a trained health worker to record treatment sideeffects. The collected blood and stool samples will be processed as initially planned. Dependent upon COVID-19 or other government restrictions, and where possible, samples may be frozen for analysis at a later date.

When COVID-19 or other government restrictions are lifted it is intended that trial activities which directly involve the participants will be carried out in the participating primary schools as initially planned. The alternative locations for trial activities are to facilitate the conduct of trial activities whilst adhering to the COVID-19 or other government restrictions, the National Guidelines for Conduct of Research during coronavirus Disease 2019 (COVID-19) Pandemic, July 2020, UNCST, Government of Uganda and the FibroScHot Risk Mitigation Plan.

12.1. Participant identification

Children attending primary schools in Hoima District, Uganda will be enrolled. Participating schools will be selected from already collected ultrasound screening data, to ensure high morbidity schools are involved, and their enrolment numbers for primaries 1 to 4, to limit the number of participating schools. Advocacy meetings will be held with District officials, including local government, Health and Education officials and with school-teachers prior to commencement of enrollment. Information meetings will be held with members of the community to explain the purpose and procedures of the trial to parents/guardians of the children. The study will also be explained to the school children themselves.

12.2. Consent

The Informed Consent form will be approved by the Vector-Control Division, Ministry of Health REC and will be in compliance with GCP, local regulatory requirements and

legal requirements. The investigator or designee will ensure that the legally acceptable representative of each trial participant is fully informed about the nature and objectives of the trial and possible risks associated with their participation.

The investigator or designee will obtain written/marked informed consent from each participant's legally acceptable representative before any trial-specific activity is performed. If the participant's legally acceptable representative is unable to read or write, the trial documentation will be read to them in the local language and their questions addressed, prior to their marking of the consent form. An independent observer will witness consent procedures for those who can't read and write. Written assent will be obtained from all children who participate in the trial, after age-appropriate description of the procedures involved. Those seeking written assent must be particularly sensitive to and prevent any pressures being applied to the children regarding their decision to participant in the trial or not. The trial information sheets and consent/assent forms will be translated into the local language, and back translated into English. All sections of the approved documents must appear in the translation. The translated version will be appropriately dated and include version control.

The informed consent form used for this trial and any change made during the course of this trial, will be prospectively approved by the REC. The Trial site co-ordinator, [name], will retain the original of each participant signed/marked informed consent and assent forms.

Any new information which becomes available, which might affect the participant's willingness to continue participating in the trial will be communicated to the participant and their legally acceptable representative at the next visit by a member of the trial team. We do not expect any new information as this drug has been available for 40 years post licensure and is not being used for any unintended purposes.

12.3. Screening evaluation

12.3.1. Screening Assessments

Trial specific assessments will only be conducted after participants and their legally acceptable representative have given their written/marked informed consent/assent.

The primary outcome of the trial will be obtained from ultrasonography examinations. They will be conducted according to the WHO Niamey Protocol for Schistosomiasis.

The secondary outcome of the trial will be obtained by collection of stool samples for egg counts by Kato-Katz.

12.3.2. Exploratory outcomes

Sample collections for the exploratory outcomes to be carried out where local conditions permit and involve:

Stool samples 4-week post-treatment egg reduction egg counts

Urine samples Pre-treatment and 4-week post-treatment CCA urinary

dip-stick diagnosis of *S. mansoni*. Parasites to be hatched

from stool samples for those positive by CCA.

Blood sample 8ml by phlebotomy for cellular and cytokine response

measurement.

ISRCTN Number: 16994599

All assessments are non-invasive (ultrasonography and stool collection), or considered of minor risk (phlebotomy).

12.3.3. Participant Registration/Randomisation

Participants will be enrolled prior to any other visits/treatment can be scheduled. Individuals will be randomised on a 1:1:1 ratio into the control or intervention arms.

12.3.3.1 Participant Photograph

A photograph of each participant is to be taken at enrolment or as soon as possible after enrolment and kept by the trial team to assist with participant identification throughout the trial. Photograph to be destroyed or handed to participant at end of trial.

